## CONFIDENTIAL

207660

RAP Section	Amendment Details
Change of functional disability	
Section 7.3.6. Time to Patient-Reported Onset of Spasticity Symptom Relief	
 
Added the derivation of time to event data in case that the participant does not complete Visit 2 and is withdrawn from study later than the planned date of Visit2.
 

Section 7.3.7. Time to Qualification for retreatment	
 
Removed ITT4 population from the time to qualification for retreatment analysis since participants who were treated 4 times were not assessed to be retreated.
 

Section 8.1.	
 
Added the plan for summary of AE within 84 days by sex and age group.
 

Section 8.3.	
 
Added the details of Worst case urinalysis.
 

Section 8.5.	
 
Added Patient Profiles analysis
 

Section 10.3 Assessment Windows	
 
Added the definition of assessment windows for efficacy analyses. The rationale was also added in the section.
 

Section 10.4.1.	
 
Changed the definition of study phases for concomitant medication.
 

Section 10.4.2.	
 
Corrected the definition of Study Phase for AE to that for which AE start time is not used since the previous definition was not that of AE which occurred within 84days.
 

Section 10.5.2.	
 
Added the plan for 95% confidence interval in summary tables for continuous efficacy endpoints.
 

Section 10.6.2 Age Category	
 
Changed the definition of Age Category to that of EudraCT requirement.
 

Section 10.12.4.	
 
Corrected the analysis population of "Summary of Race and Racial Combinations" from Enrolled to ITT1 because of baseline characteristics evaluation.
 

Section 10.12.5.2.	
 
Added the summary tables of efficacy endpoints in Open Label Phase (2nd treatment)
 

Section 10.14.	
 
Added the decision tree to determine data cutoff visit and date.
 

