### 8.1. Adverse Events Analyses

Adverse events analyses including the analysis of adverse events (AEs), Serious (SAEs) and other significant AEs will be based on GSK Core Data Standards. The details of the planned displays are provided in [Appendix 12: List of Data Displays](#).

Adverse events that occurred in the overall study period, blinded period and open-label period will be summarized for each treatment group. The treatment group is based on dose actually given in blind period. For the blinded period, 2 patterns of analyses on adverse events will be performed, one is on adverse events that occurred between the initial dose and the first dose in the open-label period (or at the completion of study if no dose is given in the open-label period or at the study withdrawal), and another one is on adverse events that occurred within 84 days from the initial dose.

Overall study period (Treatment Emergent AEs)

Blind phase

1. AEs occurred between the initial dose and the first dose in the open-label period (or at the completion of study if no dose is given in the open-label period or at the study withdrawal)
2. AEs occurred within 84 days from the initial dose

Open-label phase

- 3.01. AEs occurred during 2nd treatment cycle.
- 3.02. AEs occurred during 3rd treatment cycle.
- 3.03. AEs occurred during 4th treatment cycle.

The number and percentages of participants who experience at least one AE will be presented for each category of AE listed as below by treatment group.

- All Treatment Emergent AEs (by SOC and PT, by SOC, PT and Maximum Intensity)
- Common AEs ( $\geq 3\%$ ) (by overall frequency)
- Drug Related AEs (by SOC and PT, by SOC, PT and Maximum Intensity)
- Non-Fatal Serious AEs
- Drug Related Non-Fatal Serious AEs
- AEs Leading to Withdrawal from Study (by SOC and PT)
- Most Common Serious Drug Related AEs (by overall frequency)
- Most Common Non-Serious Drug Related AEs (by overall frequency)
- Common ( $\geq 5\%$ ) Non-Serious AEs (by SOC and PT)
  - Number of Participant and Occurrences will be presented.

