### 10.4.2. Study Phases for Adverse Events

Flag	Definition
Treatment Emergent	
 
First Study Treatment Date ≤ AE Start Date ≤ Final Visit Date/Early Withdrawal Date
 

Blind phase (until second dose)	
 
First Study Treatment Date ≤ AE Start Date ≤ Second Study Treatment Date AND AE Start Time < Second Study Treatment Time IF AE Start Time is collected
 
First Study Treatment Date ≤ AE Start Date < Second Study Treatment Date IF AE Start Time is not collect.
 

Blind phase (within 84 days)	
 
First Study Treatment Date ≤ AE Start Date ≤ First Study Treatment Date + 83 days
 

Open-Label Phase (2nd Treatment)	
 
Second Study Treatment Date ≤ AE Start Date ≤ Third Study Treatment Date AND Second Study Treatment Time ≤ AE Start Time < Third Study Treatment Time IF AE Start Time is collected
 
Second Study Treatment Date ≤ AE Start Date < Third Study Treatment Date IF AE Start Time is not collected
 

Open-Label Phase (3rd Treatment)	
 
Third Study Treatment Date ≤ AE Start Date ≤ Fourth Study Treatment Date AND Third Study Time ≤ AE Start Time < Fourth Study Treatment Time IF AE Start Time is collected
 
Third Study Treatment Date ≤ AE Start Date < Fourth Study Treatment Date IF AE Start Time is not collected
 

Open-Label Phase (4th Treatment)	
 
Fourth Study Treatment Date ≤ AE Start Date ≤ Final Visit Date AND Fourth Study Time ≤ AE Start Time IF AE Start Time is collected
 
Fourth Study Treatment Date ≤ AE Start Date ≤ Final Visit Date IF AE Start Time is not collected
 

Drug related	
 
If relationship to Study treatment(GSK1358820/Placebo) is marked 'YES' on CRF OR value is missing.
 

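### Four AE phase flags in SAP Section 10.4.2 apply a clock-time test on every day of the cycle, so timed AEs go unallocated, and last cycles are not properly closed

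*SAP*

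**What the plan says.** Section 10.4.2 gives each of the four flags two branches. If AE start time is not collected, dates alone decide. If it is collected, a date condition and a time condition must both hold:

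- **Blind phase (until second dose):** the date condition is "First Study Treatment Date ≤ AE Start Date ≤ Second Study Treatment Date". In addition, the event's clock time must be earlier than that of the second injection.
- **2nd treatment:** AE date between the second and third treatment dates. The time condition is "Second Study Treatment Time ≤ AE Start Time", and the event's hour must also be earlier than that of the third injection.
- **3rd treatment:** AE date between the third and fourth treatment dates, and "Third Study Time ≤ AE Start Time < Fourth Study Treatment Time".
- **4th treatment:** the date condition is "Fourth Study Treatment Date ≤ AE Start Date ≤ Final Visit Date". In addition, the event's clock time must be no earlier than that of the fourth injection.

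Two other flags in the same table use dates only: blind phase (within 84 days), and treatment emergent, which ends at final visit or early withdrawal.

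Section 8.1 describes the intended windows. The first blind-phase analysis covers AEs from the initial dose to the first open-label dose, "or at the completion of study if no dose is given in the open-label period or at the study withdrawal". The open-label analyses cover AEs during the 2nd, 3rd and 4th cycles.

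In the April 2018 version, the within-84-days flag also carried a time condition. The August 2018 amendment removed it, "since the previous definition was not that of AE which occurred within 84days" (Section 1.1, amendment table). The four flags above kept theirs.

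**The concern.** A clock-time comparison makes sense only on the day of an injection, where it decides whether an AE began before or after the dose. As written, it applies on every day of the cycle. An AE weeks before the second injection then depends on whether its hour of onset happens to be earlier than the hour of that injection. The same AE with no recorded time would be counted, so a more complete record is penalised.

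Counting the table lists in Sections 10.12.7.1 and 10.12.7.2, 54 AE tables rest on these four flags: 18 interim and 36 final. They cover all AEs, maximum intensity, common AEs, drug-related AEs, AESI, non-fatal serious AEs, drug-related non-fatal serious AEs and AEs leading to withdrawal. The open-label cycles have no parallel date-only tables, and Section 8.2 asks for AESI by treatment cycle.

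A second problem concerns where a cycle ends. The until-second-dose, 2nd- and 3rd-cycle flags are closed by the next treatment date, which does not exist for a participant who receives no further injection. The 4th-cycle flag ends at the final visit and does not mention early withdrawal.

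**Working it through.** The SAP gives no figure here to reproduce. The check applies the rules literally.

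**Single cases.** Section 10.2.1 (footnote f) puts V5, the first opportunity for re-treatment, at least 84 days after V1.

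- AE on Day 20 at 15:00, second injection at 10:00 at least 84 days after the first. The date condition holds. The time condition, 15:00 < 10:00, fails. The AE is not blind phase, although Section 8.1 places it there.
- Injections 2 and 3 both at 10:00. Cycle 2 needs 10:00 ≤ AE time < 10:00, which no AE can meet. The same follows whenever injection 3 is at an earlier hour than injection 2.
- Injection 2 at 10:00 and injection 3 at 14:00, onsets uniform over 24 h: cycle 2 keeps 4/24 = 17%.
- Blind phase, onsets uniform over 24 h: loss is 1 − 10/24 = 58% with injection 2 at 10:00, and 1 − 14/24 = 42% with injection 2 at 14:00.

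**General size.** Assumptions, none of them in the SAP: injection hours are independent and uniform from a to b (mean m, length L = b − a); onset hours are uniform on a window starting at s with width W that contains the injection hours. Ignoring the injection days themselves, the share of timed AEs lost is

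- until second dose: 1 − (m − s)/W
- 2nd or 3rd treatment: 1 − L/(6W), because the expected positive part of the difference between two such injection hours is L/6
- 4th treatment: (m − s)/W

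For injections 09–17 h and onsets 00–24 h these give 1 − 13/24 = 45.8%, 1 − 8/144 = 94.4% and 13/24 = 54.2%.

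A simulation of 400,000 timed AEs per scenario, with injections at 0, 84, 168 and 252 days, final visit at 336 days and uniform AE dates, includes the injection days and agrees closely. Percentage lost from the AE's own phase:

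| Injection hours | Onset hours | Until 2nd dose | 2nd | 3rd | 4th | All four |
|---|---|---|---|---|---|---|
| 09–12 | 00–24 | 56.1 | 97.9 | 97.9 | 43.4 | 73.8 |
| 09–12 | 07–22 | 76.7 | 96.7 | 96.6 | 23.3 | 73.2 |
| 09–17 | 00–24 | 45.6 | 94.4 | 94.4 | 54.1 | 72.1 |
| 09–17 | 07–22 | 59.9 | 91.0 | 90.9 | 39.9 | 70.3 |
| 13–17 | 00–24 | 37.5 | 97.1 | 97.3 | 62.2 | 73.5 |
| 13–17 | 07–22 | 46.7 | 95.5 | 95.6 | 52.6 | 72.5 |

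**Upper bounds, side by side.**

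| Flag | End in 10.4.2 | If no further injection |
|---|---|---|
| Until second dose | second treatment date | undefined in 10.4.2; Section 8.1 says completion or withdrawal |
| 2nd, 3rd treatment | next treatment date | undefined; Section 8.1 is silent |
| 4th treatment | final visit | early withdrawal not named |
| Treatment emergent | final visit or early withdrawal | complete |

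This gap affects untimed AEs as well, since the date-only branches use the same bounds.

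**The case against.** A reader might infer that most timed AEs vanish from the blind-phase tables, or that serious and toxin-spread events will be under-reported in the study report. The documents support neither. For the until-second-dose and 4th-cycle flags the loss can fall on either side of one half, depending on hours the SAP does not state. Section 8.1 plans a second blind-phase analysis, within 84 days, whose flag has no time test. The overall treatment-emergent tables are also date-only. The listings of all AEs, fatal serious AEs and non-fatal serious AEs still show each event with its study phase, so an AE without a phase would be visible there.

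Nor is it telling that cycle tables might not add up to the overall table. They count participants with at least one AE, and one participant can appear in several cycles, so they need not add up even under correct flags.

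The loss also requires a recorded start time, and the SAP does not say how many AEs will have one. The date-only branch, with its strict inequality at the next treatment date, suggests the time test was meant to settle injection-day ties, and a programmer might code it that way. That is a fair guess at intent, but Section 10.4.2 does not say it, and two people programming independently could differ.

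On the bounds, Section 8.1 does supply the blind-phase end, and the schedule in Section 10.2.1 places withdrawal in the final-visit column. However, the treatment-emergent flag names the two dates separately, and nothing closes a last 2nd or 3rd cycle.

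**Conclusion.** The rule is wrong as written and contradicts Section 8.1. If it is programmed literally, timed AEs fail to reach their own phase: nearly all in cycles 2 and 3 (about 91–98%), a substantial share until the second dose (about 37–77%) and in cycle 4 (about 23–62%). If all four injections are given at equal intervals, about 70–74% are lost across the four phases. These ranges rest on the assumed injection and onset hours; the near-total loss in cycles 2 and 3 holds in all six scenarios.

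The consequence is failed allocation to phase and cycle, including AESI and serious AEs by cycle. The within-84-days tables, the overall treatment-emergent tables and the presence of each AE in the listings are unaffected. The missing end for a last 2nd or 3rd cycle is a clear gap. The blind-phase end and the early-withdrawal omission in cycle 4 are inconsistencies to align with Section 8.1 and with the treatment-emergent flag.

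**What to change.** In Section 10.4.2:

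1. Apply the time test only when the AE start date equals the date of injection 2, 3 or 4. An AE timed before that injection goes to the earlier phase or cycle; one timed at or after it goes to the new cycle. On all other days use dates alone.
2. Keep the first-dose lower bound as a date only. A time test there would leave a Day 1 AE that began before the injection treatment emergent but in no phase.
3. If AE time is not collected, keep the present date rule at each injection date.
4. For a participant's last cycle, whichever it is, end the window at AE start date ≤ final visit date or early withdrawal date, for timed and untimed AEs alike. The bound must be inclusive so that AEs starting on that day stay in.

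The windows then run without gap or overlap from first dose to end of study, and every treatment-emergent AE with a known start date falls in exactly one phase. The cost is a few lines of text and one derivation in the AE dataset, with no new data. A programmed check that each treatment-emergent AE carries exactly one phase flag, leaving the within-84-days flag aside, would confirm it.

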**10.4.2.1. Definition of Adverse Events of Special Interest**

AEs of Special Interest are defined in the [Appendix 13](#). If a Preferred Term of AE is included in the list of PTs of the specific AESI, that AE will be considered as AESI. See the details in the [Appendix 13](#).

CONFIDENTIAL

207660

## 10.5. Appendix 5: Data Display Standards & Handling Conventions

### 10.5.1. Reporting Process

Software	

 
The currently supported versions of SAS software will be used.
 
	
Reporting Area	
HARP Server	: US1SALX00259.corpnet2.com
HARP Compound	: arenv\arprod\gsk1358820\mid207660
Analysis Datasets	

 
Analysis datasets will be created according to Legacy GSK A&R dataset standards.
 
	
Generation of RTF Files	

 
RTF files will not be generated.
 
	

### 10.5.2. Reporting Standards

General	

 
The current GSK Integrated Data Standards Library (IDSL) will be applied for reporting, unless otherwise stated (IDSL Standards Location: https://spope.gsk.com/sites/IDSLLibrary/SitePages/Home.aspx): 
 
4.03 to 4.23: General Principles
 
5.01 to 5.08: Principles Related to Data Listings
 
6.01 to 6.11: Principles Related to Summary Tables
 
7.01 to 7.13: Principles Related to Graphics
 
 
 
Do not include participant level listings in the main body of the GSK Clinical Study Report. All participant level listings should be located in the modular appendices as ICH listings
 
	
Formats	

 
GSK IDSL Statistical Principles (5.03 & 6.06.3) for decimal places (DP's) will be adopted for reporting of data based on the raw data collected, unless otherwise stated.
 
Numeric data will be reported at the precision collected on the eCRF.
 
The reported precision from non eCRF sources will follow the IDSL statistical principles but may be adjusted to a clinically interpretable number of DP's.
 
	
Planned and Actual Time	

 
Reporting for tables, figures and formal statistical analyses: 
 
Planned time relative to dosing will be used in figures, summaries, statistical analyses and calculation of any derived parameters, unless otherwise stated.
 
The impact of any major deviation from the planned assessment times and/or scheduled visit days on the analyses and interpretation of the results will be assessed as appropriate.
 
 
 
Reporting for Data Listings: 
 
Planned and actual time relative to study drug dosing will be shown in listings (Refer to IDSL Statistical Principle 5.05.1).
 
Unscheduled or unplanned readings will be presented within the participant's listings.
 
 
 
	

**CONFIDENTIAL**

207660

Unscheduled Visits	

 
• Unscheduled visits will not be included in summary tables and/or figures.
 
• All unscheduled visits will be included in listings.
 
	
Descriptive Summary Statistics	
Continuous Data	Refer to IDSL Statistical Principle 6.06.1 For continuous efficacy endpoints, 95%Confidence Interval will be calculated based on t-distribution.
Categorical Data	N, n, frequency, %
Time to event data	
 
• The number of events and censored case.
 
• 25th and 75th percentiles survival time.
 
• Median survival time with the associated 95% CIs.
 
 95%CIs will be calculated based on Brookmeyer and Crowley method using log-log function as a g-transformation. (This method can be performed using Proc LIFETEST with no special statement or option (SAS 9.4))
Graphical Displays	

 
• Refer to IDSL Statistical Principals 7.01 to 7.13.
 
	

## CONFIDENTIAL

207660

**10.6. Appendix 6: Derived and Transformed Data****10.6.1. General**

Study Day

 
• Calculated as the number of days from First Dose Date: 
 
• Ref Date = Missing → Study Day = Missing
 
• Ref Date < First Dose Date → Study Day = Ref Date – First Dose Date
 
• Ref Date ≥ First Dose Date → Study Day = Ref Date – (First Dose Date) + 1
 
 
 

**10.6.2. Study Population**

Age

 
• GSK standard IDSL algorithms will be used for calculating age where birth date will be imputed as follow: 
 
○ Any participant with a missing date and month will have this imputed as '30th June'.
 
 
 
• Birth date will be presented in listings as 'YYYY'.
 
• Age will be calculated based on year of the Screening visit as an Age reference date.
 

Age Group

 
• The following category will be used for Summary of Demography. 
 
○ Age ≤ 18 (years)
 
○ 19 < Age < 65
 
○ 65 ≤ Age
 
 
 

Age Category

 
• The following category will be used for Summary of Age Ranges. 
 
○ In utero
 
○ Preterm newborn infants (gestational age <37 weeks)
 
○ Newborns (0-27 days)
 
○ Infants and toddlers (28 days-23 months)
 
○ Children (2-11 years)
 
○ Adolescents (12-17 years)
 
○ Adult (18-64 years)
 
○ ≥65-84 years
 
○ ≥85 years
 
 
 

Extent of Exposure

 
• The total of dosage per treatment cycle will be calculated based on the formula: Total of Dosage per treatment cycle = Sum of (Dosage in each Muscle Region)
 
• The subtotal of dosage in each joint per treatment cycle will be calculated based on the formula: Subtotal of Dosage in the joint per treatment cycle = Sum of (Dosage in each Muscle Region of the Joint)
 
• Example Subtotal of Dosage in Elbow = Sum of (Dosage in Biceps brachii, Brachialis and Brachioradialis)
 

CONFIDENTIAL

207660

**10.6.3. Efficacy**

Time to Event Data
Time to Qualification for Retreatment

 
This time to event data will be derived based on the following formula:  <math display="block">\text{Time to Event (Days)} = \text{Date When a Participant Meets the Criteria for Retreatment} - \text{Study Treatment Start Date (Days)}</math> 
 
If a participant is withdrawn from this study, the participant will be regarded as censoring and censored date will be a withdrawal date.
 

Time to Patient Reported Onset of Spasticity Symptom Relief

 
This time to event data will be derived based on the following formula:  <math display="block">\text{Time to Event (Days)} = \text{Onset Date of the Spasticity Symptom Relief} - \text{Study Treatment Start Date (Days)}</math> 
 
 
If a participant is withdrawn from this study, the participant will be regarded as censoring and censored date will be a withdrawal date.

CONFIDENTIAL

207660

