## CONFIDENTIAL

207660

Overview of Study Design and Key Features	
	
muscles that act on the finger (including thumb flexors) and wrist flexors, and 160 units into the muscles that act on the elbow flexors. A total of 400 units of the product will be injected.
 
 
• In the 240-unit group, 240 units of the product will be injected into the muscles that act on the finger (including thumb flexors) and wrist flexors. Placebo will be injected into the muscles that act on the elbow flexors. A total of 240 units of the product will be injected.
 
• In the Open-label phase, a total of 400 units will be injected in both groups. 
 
• The product can be injected up to 3 times after completion of Part 1 in the blind phase. Participants whom the investigator considers as eligible for the injections will be treated. The next injections cannot be performed until the eligibility of the participant has been confirmed by the investigator.
 
• The muscle to be injected and the dose will be decided by the investigator based on the patient's symptoms, and a total dose of 400 units of the product will be injected in a divided dose. For the muscles that the investigator considers as unnecessary to be treated, an injection may be skipped. The involving muscle and the dose do not have to be same each time always.
 
 
 

Treatment Assignment	
 
• Number of participants (randomized participants): 120 (60 per group)
 
• GSK RandAll NG will be used to generate the randomization schedule.
 
• The randomization will be stratified by the MAS score (3 or 4) in the elbow flexors at Day1
 

Interim Analysis	
 
• Interim analysis is planned in this study as described in 3.1.
 

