**4. ANALYSIS POPULATIONS**

Population	Definition / Criteria	Analyses Evaluated
Screened	
 
Comprise of all screened participants
 
	
 
Study Population
 

Enrolled	
 
Comprise of all participants who meet the eligibility criteria at a screening and Day 1 visit.
 
	
 
Study Population
 

Intent-To-Treat 1 (ITT1)	
 
This population consists of all participants who are randomized in the study and who have at least 1 post-baseline efficacy assessment:
 
ITT is the primary efficacy analysis population, and the participants will be analyzed in line with the randomized treatment group
 
Any participant who receives a study treatment randomization number will be considered to have been randomized.
 
	
 
Study Population
 
Efficacy
 

ITT2	
 
This population consists of all participants in ITT1 population, who have at least 2 study treatments and who have at least 1 efficacy assessment after the 2nd treatment.
 
	
 
Study Population
 
Efficacy
 

ITT3	
 
This population consists of all participants in ITT2 population, who have at least 3 study treatments and who have at least 1 efficacy assessment after the 3rd treatment.
 
	
 
Study Population
 
Efficacy
 

ITT4	
 
This population consists of all participants in ITT3 population, who have 4 study treatments and who have at least 1 efficacy assessment after the 4th treatment.
 
	
 
Study Population
 
Efficacy
 

Safety1	
 
This population consists of all participants who are randomized in the study and who receive study treatment at least once
 
The participants will be analyzed based on the treatment actually given.
 
	
 
Safety
 

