### **7.3.6. Time to Patient-Reported Onset of Spasticity Symptom Relief**

These analyses will be based on ITT 1, 2, 3 and 4 populations.

Time to event data will be summarized using the descriptive statistics below and listed.

- The number of events and censored cases.
- Median survival time with the associated 95% CI.
- 25% and 75% survival time.

Survival analyses will be conducted using a Kaplan-Meier method. To graphically compare the survival functions between 400 units and 240 units, the analysis will be conducted based on ITT 1 population whereas the analyses will be based on ITT 2, 3 and 4 populations to assess the survival time by treatment cycle. Participants who are withdrawn from this study before Visit 2 are censored at the withdrawal date. All other participants who do not experience the event and is not withdrawn from study or of whom the date of Visit 2 is missing and is not withdrawn from study before the planned date of Visit 2 are censored at the Visit 2.

Survival function estimates will be summarized (survival probabilities and the number of participants at risk per time to event, and median in survival time) based on Kaplan Meier method. Kaplan Meier plots will be presented.

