### **7.3.7. Time to Qualification for Retreatment**

These analyses will be based on ITT 1, 2 and 3 populations.

The number and percentage of event of interest will be presented by visit. Time to event data will be summarized using the descriptive statistics below and listed.

- The number of events and censored cases.
- Median survival time with the associated 95% CI.
- 25% and 75% survival time.

Survival analyses will be conducted using a Kaplan-Meier method. To graphically compare the survival functions between 400 units and 240 units, the analysis will be conducted based on ITT 1 population whereas the analyses will be based on ITT 2 and 3 populations to assess the survival time by treatment cycle. Participants who are withdrawn from this study before the events are censored at the withdrawal date. All other participants who do not experience the event and is not withdrawn from study are censored at the Last Observed Visit at the interim analyses or the final analyses.

Survival function estimates will be summarized (survival probabilities and the number of participants at risk per time to event, and median in survival time) based on Kaplan Meier method. Kaplan Meier plots will be presented.

Note that the retreatment is not allowed within 83 days from the previous treatment. Therefore, this event will not occur before 83 days later after the treatment/re-treatment.

CONFIDENTIAL

207660

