**10.2. Appendix 2: Schedule of Activities**

**10.2.1. Protocol Defined Schedule of Events**

	Screening a	Blind phase 1) If a participant meets the eligibility at V5/ QRV, the participant will move forward to the open- label phase						Open-label phase If a participant meets the eligibility at V5/QRV, the participant will move forward to the next treatment phase						Completion visit
		Part 1					Eligibility evaluation b	Part 2/Part 3/ Part 4				Eligibility evaluation b		
Visit	SV	V1 (Day 1)	V2	V3	V4	V5 c (Eligibility evaluation)	QRV	V1	V2	V3	V4	V5 d (Eligibility evaluation)	QRV	Final Visit
Time from initial injection (Day 1) (Weeks)	—	0	2	4	6	12	Allowable Week 16 to 36 e	—	—	—	—	—	Allowable Week 24 to 36 e	48/ Withdrawal
Time from injection day in each treatment phase (Weeks)	—	0	2	4	6	12	16/ 20/ 24/ 28/ 32/ 36	0	2	4	6	12	16/ 20/ 24	-
Acceptable visit windows (days)		—	±4	±4	±4	+4 f	±14 g	(+4) v	±4	±4	±4	+4 f	±14 g	±4
Written informed consent	X h													
Randomization		X i												
Injections		X						X						
Evaluation of eligibility						X	X					X	X	
Inclusion/exclusion criteria j	X	X i												
Participant demography	X													
MAS k	X	X i	X	X	X	X	X	X i,t	X	X	X	X	X	X
NRS l		X i	X	X	X	X		X i,t	X	X	X	X		(X) r
DAS		X i	X	X	X	X		X i,t	X	X	X	X		(X) r
CGI by a investigator			X	X	X	X			X	X	X	X		(X) r
CGI by a patient			X	X	X	X			X	X	X	X		(X) r
Time to patient-reported onset of spasticity symptom relief			X						X					
Patient-reported benefit of injection				X	X	X				X	X	X		(X) r
Physical examination	X													

CONFIDENTIAL

207660

	Screening a	Blind phase 1) If a participant meets the eligibility at V5/ QRV, the participant will move forward to the open- label phase					Eligibility evaluation b	Open-label phase If a participant meets the eligibility at V5/QRV, the participant will move forward to the next treatment phase					Completion visit	
		Part 1						Part 2/Part 3/ Part 4						Eligibility evaluation b
Visit	SV	V1 (Day 1)	V2	V3	V4	V5 c (Eligibility evaluation)	QRV	V1	V2	V3	V4	V5 d (Eligibility evaluation)	QRV	Final Visit
(complete version)														

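### Appendix 6 censors every withdrawn participant at withdrawal, with no condition that the event has not yet occurred, contradicting Sections 7.3.6 and 7.3.7 (minor; exploratory endpoints)

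*SAP*

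**What the plan says.** All references are to the amended SAP.

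- **Appendix 6, Section 10.6.3**, gives a formula for each endpoint (event date minus treatment start date). After each formula it adds: "If a participant is withdrawn from this study, the participant will be regarded as censoring and censored date will be a withdrawal date".
- **Section 7.3.6 (onset of relief)**: "Participants who are withdrawn from this study before Visit 2 are censored at the withdrawal date". Others without the event who have not withdrawn are censored at Visit 2, as are those "of whom the date of Visit 2 is missing and is not withdrawn from study before the planned date of Visit 2".
- **Section 7.3.7 (qualification for retreatment)**: "Participants who are withdrawn from this study before the events are censored at the withdrawal date".
- **Section 10.2.1 (schedule)**: the row "Time to patient-reported onset of spasticity symptom relief" is marked only at Visit 2 of each treatment cycle.
- **Section 1.1 (amendment log)** records that the missing-Visit-2 rule was added on purpose, "in case that the participant does not complete Visit 2 and is withdrawn from study later than the planned date of Visit2".

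The SAP does not say which text governs when Appendix 6 and Section 7.3 differ.

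**The concern.** Appendix 6 is where a programmer looks for the derivation, and its withdrawal sentence has no qualifier. Taken at its word, a participant with onset on Day 5 who withdraws after Visit 2 is coded as censored at withdrawal. The recorded onset disappears because of something that happened later. The same holds for a participant who qualified for retreatment at Week 12 and withdrew afterwards.

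An event lost this way also leaves the participant in the risk set throughout the period when events occur. The event-free curve can therefore only rise, and any error is towards later onset or later qualification. If withdrawal differs between arms, so does the error.

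**Working it through.** **1. The three rules applied to the same participants**

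| Participant | Appendix 6, literal | Section 7.3.6 or 7.3.7 |
|---|---|---|
| Onset recorded at Visit 2, withdraws later | Censored at withdrawal | Event kept |
| Qualifies at Week 12, withdraws later | Censored at withdrawal | Event kept |
| Visit 2 attended, no onset, withdraws later | Censored at withdrawal | Not covered by 7.3.6 |
| Withdraws before Visit 2 | Censored at withdrawal | Censored at withdrawal |

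The first two rows are the contradiction. The third is a gap in Section 7.3.6.

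**2. Size for onset of relief**

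The SAP states no onset or withdrawal rate, so there is no plan figure to reproduce. Inputs:

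- 60 per arm (Section 2.3).
- e = proportion with onset by Day 14. Assumed 0.60 or 0.80.
- w = proportion withdrawing after Visit 2, unrelated to onset. Assumed 0.05 to 0.20.

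Under the literal rule these withdrawers stay at risk through Day 14 and contribute no events:

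- Event-free at Day 14 = 1 − e(1 − w), against a true 1 − e.
- Events lost per arm = 60 × e × w.

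| e | w | True | Literal rule | Shift | Events lost of 60 |
|---|---|---|---|---|---|
| 0.60 | 0.05 | 0.40 | 0.43 | 0.03 | 1.8 |
| 0.60 | 0.10 | 0.40 | 0.46 | 0.06 | 3.6 |
| 0.60 | 0.20 | 0.40 | 0.52 | 0.12 | 7.2 |
| 0.80 | 0.05 | 0.20 | 0.24 | 0.04 | 2.4 |
| 0.80 | 0.10 | 0.20 | 0.28 | 0.08 | 4.8 |
| 0.80 | 0.20 | 0.20 | 0.36 | 0.16 | 9.6 |

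A simulation with exponential onset times and 200,000 participants agrees. At w = 0.10, relief by Day 14 is 0.540 for e = 0.60 and 0.720 for e = 0.80. The median moves from 11 to 13 days and from 7 to 8 days respectively.

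If both arms have e = 0.80 but withdrawal is 5% in one and 15% in the other, the rule alone produces a difference of 0.80 × (0.95 − 0.85) = 0.08.

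**3. Interim against final for qualification**

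Take a participant who qualifies at Week 12 and withdraws at Week 30. The interim uses data up to the Week 24 visit (Section 3.1), so Table 2.23 shows an event at Week 12. At the final analysis the participant is a withdrawal, so under the literal rule Table 2.51 shows a censored time at Week 30. The blind-phase data are identical. If retreated and assessed, the same person is also in ITT2, which requires a second treatment (Section 4).

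**4. The two smaller items**

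- *Post-Visit-2 gap.* Onset is collected only at Visit 2 (Week 2 ± 4 days), and a Kaplan-Meier curve changes only at event times. Censoring at withdrawal instead of Visit 2 matters only within the few days over which Visit 2 dates spread.
- *Missing Visit 2.* ITT1 takes participants "who have at least 1 post-baseline efficacy assessment", so someone who missed Visit 2 but attended later is analysed and counted event-free to Visit 2. If 2 of 60 are in this position and the true event-free proportion is 0.20, the estimate is (0.20 × 58 + 2)/60 = 0.227.

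**The case against.** The best defence is that Appendix 6 is shorthand. It gives the event-time formula first, and the withdrawal sentence can be read as applying to people without an event date. Section 7.3.7 has the right condition, Section 7.3.6 stops withdrawal censoring at Visit 2, and Section 10.7.1 puts available planned data from withdrawn participants into tables and figures. A programmer working from Section 7.3 would lose no recorded event. This stands as a limit on the harm. It does not remove the contradiction: Section 10.7.1 yields where something else is specified, and Appendix 6 arguably specifies something else.

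A reader might infer that 48 weeks of withdrawals distort the randomised comparison of onset. The display list does not support that. The blind-phase onset Kaplan-Meier table and figure (Table 2.19, Figure 2.20) are interim outputs only, with data to Week 24. Later withdrawals can reach the final onset outputs (Tables 2.45 to 2.48) and the final qualification tables (2.51 to 2.53). Of the final onset outputs, only Table 2.45, a summary of event counts and percentiles, is on ITT1.

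A reader might also take the missing-Visit-2 rule for an error. It is a documented choice, it resembles the non-responder handling of MAS in Section 10.7.2, and a usable date is implied: Section 7.3.6 refers to the planned Visit 2 date, and Section 10.5.2 uses planned time for derived parameters. Stating that date outright would be enough.

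**Conclusion.** The contradiction is real and lies in current text. Appendix 6, read literally, is a wrong rule because it erases events already recorded. Its effect is conditional. If Appendix 6 is coded as written, and with the assumed rates of 10% withdrawal after the event window and 60% to 80% onset by Day 14, the event-free estimate rises by 6 to 8 points and about 4 to 5 events per arm are lost. At 5% withdrawal the shift is 3 to 4 points. If Sections 7.3.6 and 7.3.7 are followed, the shift is zero. No size is given for qualification, because the timing of withdrawal relative to later events would also have to be assumed.

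The documents do not support saying that the planned analysis is biased late, only that one of two conflicting instructions would make it so. Both endpoints are exploratory (Section 2.2), no hypothesis is tested (Section 2.4), and the primary endpoint is untouched. Severity: minor.

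**What to change.** 1. In Section 10.6.3, replace both withdrawal sentences with: *A recorded event counts as an event regardless of later withdrawal. A participant withdrawn before the event is censored at the withdrawal date, and for onset of relief at the earlier of withdrawal and Visit 2 of that cycle.*
2. Align Section 7.3.6 with this, so that it covers participants who attend Visit 2 without onset and withdraw later.
3. In Section 7.3.6, state that when Visit 2 is missing the censoring date is the planned Visit 2 date of that cycle, and report the number of such participants per arm. Censoring them at injection is optional, as a sensitivity analysis.

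The cost is a few sentences in the SAP and a small program change. No new data are needed and participants are not affected.
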